11.6 Participant population

Analyses will be carried out on an intention to treat basis according to randomised treatment.

11.7 Procedure(s) to account for missing or spurious data

The main analyses will be based on morbidity/mortality data for which imputation is not necessary. For quality of life outcomes, laboratory results or other continuous variables results will be analysed with and without imputation. Multiple imputation procedures will be used. Full details will be provided in the statistical analysis plan.

11.8 Other statistical considerations

A Statistical Analysis Plan (SAP) for each phase of the trial will be maintained and approved as a version controlled document prior to each formal statistical analysis. The SAP will contain full details of all analyses along with assumptions and procedures for handling problematic or incomplete data (e.g. incomplete dates).

11.9 Economic evaluation

No formal economic evaluation will be included in the statistical analysis plan, however quality of life and hospitalisation data will be collected and may be utilised in a separate economic analysis at a later date if required.

Version 5.0 22 July 2021 Page 61 of 82

12. DATA MANAGEMENT

12.1 Source Documentation

ICH GCP defines source data as: 'All information in original records and certified copies of original records of clinical findings, observations or other activities in a clinical trial necessary for the reconstruction and evaluation of the trial'. In this trial, the location of the majority of the source data will be the hospital's medical records including subject case notes, laboratory records and ECGs. The source data transcribed into the eCRF from the medical records must be accurate and verifiable. For questionnaires completed by trial subjects, the completed questionnaires will be regarded as the source data location. In cases where data is transcribed directly into the eCRF and no other paper or electronic source exists, then the eCRF will be considered the source record. In these cases, these data should be prospectively documented in the medical records to ensure a full record of the trial is available at site.

12.2 Data collection

An eCRF, developed by the Robertson Centre for Biostatistics, will capture all data required to meet this protocol's requirements. Access to the eCRF will be restricted, via a trial-specific web portal, and only authorised site-specific personnel will be able to make entries to their patients' data via the web portal. The Investigator or his /her designee will be responsible for all entries into the eCRF and will confirm that the data are accurate, complete and verifiable. Data will be stored in a MS SQL Server database.

Direct access to the web portal will be granted, on request, to authorised representatives from the Sponsor, host institution and the regulatory authorities to permit trial-related monitoring, audits and inspections.

12.3 Data Validation

Where it is practical, data will be validated at the point of entry into the eCRF. Any additional data discrepancies will be flagged to the investigator and any data changes will be recorded to maintain a complete audit trail (reason for change, date change made and who made the change).

12.4 Data Security

The Robertson Centre for Biostatistics systems are fully validated in accordance with industry and regulatory standards, and incorporate controlled access security. High volume servers are firewall protected and preventative system maintenance policies are in place to ensure no loss of service or data. Web servers are secured by digital certificates. Data integrity is assured by strictly controlled procedures, including secure data transfer procedures. Data are backed up on-site nightly and off-site to a commercial data vault weekly. The Robertson Centre for Biostatistics has an ISO 9001:2008 quality management system and ISO 27001:2013 for Information Security, and is regularly inspected against the standards by the British Standards Institution.

12.5 Archiving

The Trial Master File will be archived by the Sponsor at the end of the trial for a minimum period of 25 years.

Archiving of Site Files will also be for a minimum of 25 years from completion of the trial, and this action will be delegated to the sites in the Clinical Trial Site Agreement that will be put in place between Sponsor and Sites. Sites will be notified by the Sponsor when Site files can be archived. Destruction of site files can only take place with the approval of the Sponsor.

Version 5.0 22 July 2021 Page 62 of 82

13. MONITORING, AUDIT & INSPECTION

Trial monitoring visits will be conducted by NHS GG&C monitor(s). Prior to starting the trial, a trial-specific Monitoring Plan will be developed by the monitor(s). The level of monitoring, on-site and remote, will be based on the outcome of the completed monitoring risk assessment, and will be clearly documented in the monitoring plan which will be approved by the NHS GG&C Research Governance Manager / Academic Lead Clinical Trial Monitor. As standard, monitoring visit(s) will cover site file review, review of Informed Consent Forms (ICFs), Source Data Verification (SDV) and Serious Adverse Event (SAE) review as per monitoring plan objectives.

Central monitoring objectives will be documented in the monitoring plan upon agreement between the RCB and the Sponsor.

The CI and other investigators shall be accessible for monitoring visits. Direct access to patient records for source data verification will need to be granted and prepared prior to any monitoring visits.

Version 5.0 22 July 2021 Page 63 of 82

14. ETHICAL AND REGULATORY CONSIDERATIONS

14.1 Research Ethics Committee (REC) review and reports

Before the start of the trial, approval will be sought from a REC for the trial protocol, informed consent forms and other relevant documents e.g. advertisements and GP information letters.

Substantial amendments that require review by REC will not be implemented until the REC grants a favourable opinion for the trial (it is noted that amendments may also need to be reviewed and accepted by the MHRA and/or NHS R&D departments before they can be implemented in practice at sites).

All correspondence with the REC will be retained in the Trial Master File/Investigator Site File.

An annual progress report (APR) will be submitted to the REC within 30 days of the anniversary date on which the favourable opinion was given, and annually until the trial is declared ended (this is the Chief Investigator's responsibility).

The Chief Investigator will notify the REC of the end of the trial.

If the trial is ended prematurely, the Chief Investigator will notify the REC, including the reasons for the premature termination

Within one year after the end of the trial, the Chief Investigator will submit a final report with the results, including any publications/abstracts, to the REC.

14.2 Peer review

The trial protocol was reviewed by the British Society for Heart Failure sub-committee and at two UK Heart Failure Investigators Research Network meetings during 2018. Members have expertise in the care of patients with heart failure and/or the conduct of clinical trials in the relevant population. The protocol has also been reviewed by representatives of the funder (Vifor) and of the sponsor.

14.3 Public and Patient Involvement

The trial was designed by physicians with expertise in managing heart failure supported by the Robertson Centre for Biostatistics research design service.

A patient panel was convened to review the trial design and protocol. The design and protocol were revised in the light of their comments.

Patients will advise on the patient information sheet and enrolment strategy.

Patient organisations will disseminate information about the ongoing trial and, in due course, its results.

Guidance on involving patients and the public in research can be found on the INVOLVE website. http://www.invo.org.uk/

14.4 Regulatory Compliance

 The trial will not commence until a Clinical Trial Authorisation (CTA) and a favourable opinion is obtained from the MHRA and REC, respectively.

Version 5.0 22 July 2021 Page 64 of 82

• The protocol and trial conduct will comply with the Medicines for Human Use (Clinical Trials) Regulations 2004 and any relevant amendments.

14.5 Protocol compliance

Prospective, planned deviations or waivers to the protocol are not allowed under the UK regulations on Clinical Trials and must not be used e.g. it is not acceptable to enrol a participant if they do not meet the eligibility criteria or restrictions specified in the trial protocol. Accidental protocol deviations can happen at any time. They will be adequately documented on the relevant forms and reported to the Chief Investigator and Sponsor immediately. Deviations from the protocol that frequently recur are not acceptable and will trigger immediate action and could potentially be classified as a serious breach.

14.6 Notification of Serious Breaches to GCP and/or the protocol

A "serious breach" is a breach which is likely to affect to a significant degree:

- 1. the safety or physical or mental integrity of trial participants; or
- 2. the scientific value of the trial

If any of the above occurs then the CI and Sponsor will be notified. The sponsor will notify the appropriate authorities in writing of any serious breach in accordance with their standard operating procedures.

14.7 Data protection and patient confidentiality

All investigators and trial site staff must comply with the requirements of the Data Protection Act 2018 with regards to the collection, storage, processing and disclosure of personal information and will uphold the Act's core principles.

- Personal information will be collected via the eCRF to enable record linkage to be carried out and to provide electronic access to trial monitors to a copy of the signed informed consent document. These data items will be encrypted and only those individuals who require to see these data i.e. the person performing the record linkage and site research team staff or the trial monitor, as appropriate, will be able to view them. All electronic data will be held securely in accordance with ISO 27001:2013 at the Robertson Centre for Biostatistics, part of the Glasgow Clinical Trials Unit. All Centre staff are required to sign confidentiality agreements and to follow Standard Operating Procedures in accordance with Good Clinical Practice and ISO certification.
- Only those that have been trained and approved will be able to enter or view any data via the web portal. Each site can only see their own patients' data.

14.8 Financial and other competing interests for the chief investigator, PIs at each site and committee members for the overall trial management

[name] and [name] have received honoraria from Vifor Pharma for advisory boards and speaking at meetings.

Vifor are funding the trial and supplying patiromer.

If new competing interests develop, either due to changes in the status of existing trial personnel or to the inclusion of new personnel, this will be documented in the trial master file.

Version 5.0 22 July 2021 Page 65 of 82

14.9 Indemnity

The Co-Sponsors (University of Glasgow and Greater Glasgow Health Board) will ensure that provision has been made for insurance or indemnity to cover the liability of the investigator and sponsor which may arise in relation to the clinical trial in accordance with Part 2 (14) of Schedule 1 to SI 2004/1031.

Clinical negligence will be covered by the Clinical Negligence and Other Risks Indemnity Scheme in Scotland, and the equivalent schemes in other UK countries.

The Insurance cover will be subject to the appropriate authorisations being received from the MHRA, Ethics, and the NHS.

14.10 Amendments

Any change in the trial protocol will require an amendment. Any proposed substantial protocol amendments which may impact on the safety of patients or integrity of the trial will be initiated by the CI following discussion with the Sponsor and TSC and any required amendment forms will be submitted to the regulatory authority, ethics committee and Sponsor. The Sponsor will determine whether an amendment is non-substantial or substantial. All amended versions of the protocol will be signed by the CI and Sponsor representative. Following a substantial amendment, favourable opinion/approval must be sought from the original reviewing REC, MHRA (where appropriate) and Research and Development (R&D) office prior to implementation. The Chief Investigator will be responsible for informing the Trial Management Group of all protocol amendments.

14.11 Post trial care

Patiromer and both MRA are already licensed for use in the UK.

At the end of the trial, participants will be returned to usual care as defined by local and national guidelines at that time. The results of the trial may of course have an impact on these guidelines and the future care of patients with heart failure.'

Spironolactone and eplerenone are generic medicines that are already widely prescribed.

14.12 Access to the final trial dataset

The data will be held securely at the Robertson Centre for Biostatistics at the University of Glasgow where it may be accessed by approved data-managers, statisticians and the Chief Investigator.

A full data-set may be shared with the funder after the trial is complete.

After the primary results have been published, data-sets may also be shared with co-investigators and others working in this field. This is subject to submission of a detailed statistical analysis plan, evidence of appropriate clinical and statistical expertise to support the analysis and its interpretation. Submissions must be approved by the TSC. Where data are shared, a data sharing agreement will be required which will detail requirements to ensure secure disposal after the analysis is complete. The TSC will oversee and coordinate manuscript proposals.

Version 5.0 22 July 2021 Page 66 of 82

15. DISSEMINATION POLICY

15.1 Dissemination policy

The University of Glasgow will own the data arising from the trial.

On completion of the trial, the data will be analysed and tabulated. The Steering Committee will publish the primary manuscript and review proposals for further analyses. Participating investigators will be invited to propose secondary manuscripts, with priority given to those who have enrolled many patients. Colleagues who have not participated should seek 'sponsorship' from a participating investigator in order to submit a proposal. Timelines for analyses, manuscript writing and review will be agreed on a case-bycase basis subject to available resources. The sponsor and funder should be acknowledged in all publications.

Participants will be informed of results by a newsletter and may request information about the trial results after publication.

The trial protocol will be made publicly available prior to publication on a clinical trials website.

15.2 Authorship eligibility guidelines and any intended use of professional writers

The primary manuscript will be authored by the Steering Committee and the Principal Investigators from sites providing high quality data on a substantial number of patients.

The Steering Committee will delegate authorship to investigators and other colleagues after considering their proposals.

We do not intend to use professional writers for the peer-reviewed manuscripts describing the results. The funder may wish to employ professional writers for the 'commercial' press and will acknowledge any services paid for.

Version 5.0 22 July 2021 Page 67 of 82

16. APPENDICES

Appendix 1: Risk

☐ LOW = Comparable to the risk of standard medical care							
MODERATE Somewhat higher than the risk of standard medical care							
☐ HIGH ≡ Markedly higher than the risk of standard medical care							
treatment for congest used . There are risks (hype	ion. Patiromer reduces	used for patients with he serum potassium, allow	wing higher dos) and benefits (r	es of MRA to be			
improvement in symp	toms, reduction in mor	rtality) to use of higher o	loses of MRA.				
Patiromer might caus hyperkalaemia.	e hypokalaemia, altho	ugh this is unlikely in a p	oopulation highl	y prone to			
What are the key risk therapeutic intervention monitor in this trial?		How will these risks t	oe minimised?				
IMP/Intervention	Body system/Hazard Activity Frequency Comments						
Patiromer	Hypokalaemia	Monitoring serum potassium					
MRA	Hyperkalaemia						
MRA	Symptomatic hypotension	. •					
MRA	Renal dysfunction	. •					
An IDMC will monitor patient-safety. Treatment is not blinded and therefore investigators may identify safety issues.							
Outline any processes that have been simplified based on the risk adapted approach.							
All IMP will be labelled for trial use only, including the nature of the IMP, its dose and the number of sachets/pills.							
The trial is not blinded. Patients and investigators will know what is prescribed.							
Patients in the control group will receive MRA only. Patients in the intervention group will receive patiromer and MRA.							

Version 5.0 22 July 2021 Page 68 of 82

Appendix 2: Symptom Questionnaire

Patient ID	Today's Date			
Symptoms	Score using any number between 0 and 9			
With 0 meaning no problem or none,	5 meaning troublesome and 9 being severe			
Breathlessness				
Running (score 9 if you don't run bec				
On moderate exertion (e.g. walking q	uickly, climbing 2-3 flights of stairs)			
On mild exertion (e.g. walking slowly				
On slight exertion (washing or dressing	ng)			
Sitting at rest				
Do you get breathless lying flat?				
Other Symptoms				
Swelling of Ankles				
Swelling of Legs Above Ankles				
Are you troubled by tiredness during	the day?			
Do you suffer much from anxiety?				
Do you feel depressed?				
Chest Pain on Exertion				
Dizziness				
Palpitations				
Muscle Aches & Pains				
Cough and/or Wheeze				
Other Symptom or Problem (Name)				
Other Symptom or Problem (Name)				
Quality of Life (with 1 = very good,	5 = average, 9 = very bad)			
How do you rate your health?				
How do you rate your overall quality of				
Please also answer these question				
How many pillows do you sleep with?				
Do you sometimes wake in the night				
If so, how many nights in the last two months?				
Have you had any falls?				
If so, how many in the last two month	s?			
Have you had any blackouts?				
If so, how many in the last two month	s?			

Version 5.0 22 July 2021 Page 69 of 82

Appendix 3: Managing Discontinuation of Patiromer or MRA

[figure not shown]
Patients who stop patiromer should have the dose of MRA adjusted to prevent hyperkalaemia. If serum potassium is in the normal range, the dose of MRA should be halved or reduced to 25mg/day, whichever is higher. Serum potassium should be re-checked in 7-12 days.

Patients who stop their MRA should have the dose of patiromer adjusted to prevent hypokalaemia. Many patients will be on other potassium retaining treatments and may still benefit from patiromer. If serum potassium is in the normal range, stop patiromer and re-check serum potassium in 7-12 days. If serum potassium exceeds 5.0mmol/L, patiromer should be re-started.

Version 5.0 22 July 2021 Page 70 of 82

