8.1.2 Schedule of Procedures for the Randomised Trial (long-term follow-up)

		Majority of care at follow-up in clinic									
Visit	T7	T8	T9	T10	T11	T12	T13	T14	TX	EOS	
Months	3	6	9	12	15	18	21	24	+3		
Window +/- days	14	14	14	14	14	14	14	14	14	NA	
Consent											
History											
Symptoms/NYHA	Х	Х	Х	Х	Х	Х	Х	Х	Х	Х	
PGA	Х	Х	Х	Х	Х	Х	Х	Х	Х	Х	
CV Therapy	Х	Х	Х	Х	Х	Х	Х	Х	Х	Х	
Non-CV Med		Х		Х				Х			
Height											
Weight	Х	Х	Х	Х	Х	Х	Х	Х	Х	Х	
Vital Signs	Х	X*	Х	Χ*	Х	Х	Х	Χ*	Х	Х	
Physical Exam											
Oedema Grade	Χ	X	X	X	X	X	X	X	Х	X	
Orthopnoea Test		X		X				X			
ECG trace											
Electronic ECG		X		X				X			
Echocardiogram		Opt		Opt				Opt			
Haematology		X		X				X			
Biochem Safety	Χ		X		Χ	X	Χ		X	X	
Biochem+		Х		X				X			
Spot Urine		X		Х				Х			
Biomarkers		Х		Х				Х			
KCCQ/EQ5D		Х		Х				Х			
Walk Test @		Х		Х				Х			
Titration/Compliance	Χ	Х	X	X	Χ	Χ	Χ	X	X	X	
AE/ SAE	Х	Х	Х	Х	Х	Х	Х	Х	X	X	
Dispensing	Χ	X	X	X	Χ	Х	Χ	X	Х		

T = titration visit. TX = repeat visits every 3 months for dispensing and titration. EOS = end of trial. CV = cardiovascular. X* vital signs measured during orthopnoea (orthop) test. Opt = optional

KCCQ = Kansas City Cardiomyopathy Questionnaire. EQ5D = EuroQol 5-dimension questionnaire. NYHA = New York Heart Association functional class. PGA = patient global assessment on a 7-point scale ranging from much worse to much better.

@ for patients who feel unable to do these tests, the reason will be recorded. AE / SAE = adverse / serious adverse events.

Key visits for the assessment of clinical efficacy and endpoints are

- Day 7 (+/-3 days or discharge from hospital or day-care)
- Day 60 (+/-14 days)
- And at 6 months (+/-14 days) months,12 months (+/- one month) and 24 months (+/- one month)

Additional visits are required to assess symptoms and safety (serum potassium/magnesium, renal function, blood pressure). Patients may be evaluated in the community or clinic setting as convenient but will have to attend hospital visits to obtain trial IMP (patiromer, spironolactone/eplerenone).

In addition, if doses of patiromer or MRA are changed, blood pressure and serum electrolytes and creatinine should be re-checked both after 7-12 days and after 30-45 days. If the patient becomes acutely unwell for any reason, blood pressure, serum electrolytes and creatinine should be re-checked. Serum potassium should also be checked within 48 hours of stopping patiromer.

Version 5.0 22 July 2021 Page 30 of 82

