8.9 Withdrawal criteria

Participants may choose to withdraw at any time, either from the intervention (patiromer or MRA), the follow-up procedures or from follow-up through their electronic medical record. Reasons for withdrawal will be recorded, providing the participant agrees. Participants who withdraw from the intervention or

Version 5.0 22 July 2021 Page 42 of 82

follow-up procedures should cease to take IMP and revert to standard-care. The costs of patiromer or MRA would no longer be reimbursed from the trial budget.

Participants who choose to stop patiromer-IMP only should have the dose of MRA adjusted to prevent hyperkalaemia. Participants who choose to stop MRA-IMP only should have the dose of patiromer adjusted to prevent hypokalaemia. Further guidance is provided in Appendix 3. Changes in serum potassium and clinical status should be evaluated carefully after any dose adjustments.

Participants may be withdrawn from IMP by their investigators if deemed appropriate (e.g. the investigator is concerned about a participant's safety because of uncertainty about adherence to IMP). Safety will be assessed by research nurses and/or investigators at each visit and after the occurrence of each SAE/SAR. Participants who have had an SAR (e.g. a hospital admission for the management of hyper- or hypo-kalaemia) should be reassessed for their ability to understand and comply with IMP dosing instructions.

- If the participant is, in the investigator's opinion, no longer able or willing to comply with treatment instructions, then they should stop one or both IMP and revert to standard-care, even if they have not experienced an SAE or SAR.
- Participants who are assigned to patiromer and who have or develop hyperkalaemia (serum potassium >5.0mmol/L), even if they have been withdrawn from spironolactone or eplerenone IMP, may continue on or restart patiromer.

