- amoxicillin, cephalexin, trimethoprim* (* increased risk of hyperkalaemia)
- apixaban, rivaroxaban, and warfarin.

This list may be extended as further research becomes available.

Note that at the current time there is no information available on co-administration with eplerenone therefore administration should be separated from patiromer by at least 3 hours.

Missed and omitted patiromer doses

Participants should not discontinue treatment without consulting the research team.

If a dose of patiromer is missed, it should be taken as soon as possible on the same day unless it is almost time to take the next dose in which case you should not take the forgotten dose. A double dose

Version 5.0 22 July 2021 Page 48 of 82

should not be taken on the following day to make up for a missed dose. Participants should just resume taking their next normal dose at their usual time. If doses of patiromer are missed on more than two consecutive days, participants **must** contact the research team for advice. Participants must not discontinue patiromer without consulting the trial team. Increases in serum potassium may occur within 2-4 days after the last dose of patiromer.

If the participant stops patiromer for any reason, they must also stop their MRA and contact the investigator.

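### Cheap improvement: after patiromer stops, the visible text ties no potassium check to about days 3–6, although the protocol expects a possible rise at 2–4 days and may keep the MRA going

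*Protocol*

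**What the plan says.** Potassium checks linked to stopping patiromer appear in three places in the protocol.

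- Section 8.1.2, repeated in the footnote to the titration tables in section 9.7: "Serum potassium should also be checked within 48 hours of stopping patiromer". After any change in patiromer or MRA dose, blood pressure, electrolytes and creatinine "should be re-checked both after 7-12 days and after 30-45 days".
- Appendix 3, for patients who stop patiromer: "If serum potassium is in the normal range, the dose of MRA should be halved or reduced to 25mg/day, whichever is higher", followed by "Serum potassium should be re-checked in 7-12 days". It does not repeat the 48-hour check.
- Section 8.9, without a day: "potassium and clinical status should be evaluated carefully after any dose adjustments".

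On timing, section 9.8 states: "Increases in serum potassium may occur within 2-4 days after the last dose of patiromer". The same section tells the participant: "If the participant stops patiromer for any reason, they must also stop their MRA and contact the investigator".

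Section 8.1.2 also has an event-driven safeguard: "If the patient becomes acutely unwell for any reason, blood pressure, serum electrolytes and creatinine should be re-checked".

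**The concern.** The protocol says when potassium may climb after the last dose, but the checks it ties to stopping fall mainly before and after that period. The early check also carries weight: under Appendix 3 a normal potassium is the condition for continuing the MRA at a reduced dose. A value taken within 48 hours can be normal because patiromer is still acting.

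Continuing the MRA without patiromer is a foreseen path. Section 8.9 has the MRA dose adjusted when patiromer alone is stopped, and section 9.13 lets investigators consider withdrawing patiromer for poor compliance and returning to MRA alone. Every participant was randomised with potassium above 5.0 mmol/L, and section 3 names stopping one agent without the other as an important risk. What is at stake is an undetected rise in potassium, over several days, in a patient prone to hyperkalaemia who is still taking an MRA.

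**Working it through.** The plan gives no figure to reproduce. The check compares time windows and applies the Appendix 3 dose rule.

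**Inputs**
- Early check: within 48 hours of stopping (8.1.2; 9.7 footnote).
- Later checks: 7–12 and 30–45 days after a dose change (8.1.2; 9.7 footnote); 7–12 days only in the Appendix 3 text.
- Possible rise: 2–4 days after the last dose (9.8).
- MRA dose kept if potassium is normal: max(dose ÷ 2, 25 mg/day) (Appendix 3).
- Expected median spironolactone dose in the patiromer arm: about 100 mg/day (section 2).

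**Step 1: clock started at the last dose.** Assume that stopping counts as a dose change and that the MRA is changed the same day.
- Checks fall in days 0–2, 7–12 and 30–45. Days 3–6 have none.
- Overlap with the 2–4 day window: day 2 at most, and only if the early check is done at its limit.
- Interval from a day-2 check to the next: 7 − 2 = 5 to 12 − 2 = 10 days.
- Interval from the end of the window to the next check: 7 − 4 = 3 to 12 − 4 = 8 days.

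**Step 2: clock started at the first omitted dose.** Patiromer is taken once daily, so the first omitted dose is about one day after the last dose. The 48-hour limit then reaches about day 1 + 2 = 3 after the last dose. With the later check still due from day 7, the gap narrows to about days 4–6. Day 4 of the protocol's own window is still untested.

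**Step 3: MRA dose left in place.**

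| MRA dose at stop (mg/day) | Half | Dose kept (mg/day) |
|---|---|---|
| 200 | 100 | 100 |
| 100 (expected median) | 50 | 50 |
| 50 | 25 | 25 |
| 25 | 12.5 | 25 (no reduction) |

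The rule stops the MRA at none of these doses. Section 9.7 raises spironolactone in the run-in through 25, 50 and 100 mg/day. A participant who qualified on 50 mg/day and later reached 100 would therefore return to the dose at which potassium first exceeded 5.0 mmol/L, now without patiromer.

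**Step 4: who is exposed.** Section 9.8 takes the participant off the MRA and brings them to the investigator. Exposure begins only if the investigator then continues or restarts the MRA under Appendix 3 or section 8.9.

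**Step 5: other safeguards.** The Day 3, 5 and 7 tests in section 9.7 count from randomisation, so they follow a stop only by coincidence. The acute-illness recheck needs the patient to become unwell first. Section 8.9 gives no day. Contact after more than two missed days (9.8) is for advice, with no potassium test specified.

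**The case against.** The strongest objection is that the risk is already largely handled. The participant's own instruction is to stop both drugs and call. An investigator who then continues the MRA has a check within 48 hours, further checks at 7–12 and 30–45 days, a recheck in acute illness and a general duty to evaluate potassium with care. This stands as a limit on who is exposed. It does not supply a test at the time the protocol says potassium may rise.

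Second, the interval matches the rest of the plan: a control patient with potassium of 5.0–5.9 mmol/L has the MRA reduced and is rechecked at 7–12 days. That shows the interval was not careless. But in the control patient the one change lowers potassium. Here a potassium-lowering drug is withdrawn at the same time as the MRA is reduced, or left at 25 mg/day, so the net direction is uncertain.

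Third, stopping and last dose may differ by about a day. This is accepted, and the gap is given both ways.

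Fourth, Appendix 3 contains a figure that is not available here, which could already set an earlier check. The point therefore covers the visible text only.

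A reader might also infer more than the documents support:
- *That nothing is checked before day 7.* Appendix 3 read alone suggests this, but the 48-hour check in 8.1.2 and 9.7 rules it out.
- *That 9.8 and Appendix 3 contradict each other.* They can be read as a sequence: the participant stops the MRA and calls, then the investigator decides the dose. The text does not say so, but nothing in it prevents that reading.
- *That a given number of hyperkalaemia events would follow.* The documents do not say how far potassium rises by days 3–6.

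**Conclusion.** The point holds as a low-cost safety improvement, not as an error in the plan. No potassium check in the visible text is tied to about days 3–6 after the last patiromer dose, or about days 4–6 on the alternative clock. On the last-dose clock, the next required check comes 3–8 days after the stated rise window ends. The early result can therefore support continuing an MRA before that window has closed.

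This rests on three assumptions: stopping patiromer counts as a dose change, the MRA decision is made the same day, and the Appendix 3 figure does not already add a check. A later restart of the MRA would move the 7–12 day check later as well. The SAP (section 1.6.1) records closure with four participants randomised, so the point has no bearing on this trial's results and matters for the protocol as written and any reuse of it.

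**What to change.** Keep the 48-hour check. In section 8.1.2, the section 9.7 footnote and Appendix 3, add one sentence: any participant who continues or restarts an MRA after stopping patiromer has potassium measured 3–5 days after the last patiromer dose, and the MRA dose is reviewed against that result. Counting from the last dose also removes the ambiguity over when the clock starts.

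The cost is one routine blood test, and possibly a visit, for each such discontinuation. No MRA interruption is imposed beyond what section 9.8 already asks of the participant. If the Appendix 3 figure already contains this check, the only change needed is to bring the text of the three places into line with it.
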